## **VI). Process of randomization and treatment double blinding**

The un-blinded study biostatistician, [name], will create a list of patient identification numbers with randomized treatment assignments (A = Active/Real, B = Sham) using the SPSS software prior to the start of the study subject recruitment. Blocked randomization will be used with random block size of 3 or 6. Separate lists (up to 12) of replacement patient identification numbers will also be created so that replacement patients are assigned the same treatment as patients they are replacing. Patients will be randomized to study treatment groups in a 1:1 ratio. [name] will be contacted by the study coordinator with subjects' unique master ID number (sequential number, independent from any protected health information or any other identification source) and their descriptive information. After a subject signs the study consent, the study coordinator will be provided with that subject's randomization code. A minimization random assignment procedure will be used to match subjects on four variables: 1) mechanisms of injury; 2) gender; 3) severity of headache, and 4) past failed therapies for their headache. The minimization random assignment procedure aims to obtain equal numbers of subjects at the different levels of each matching variable. In contrast to stratified randomization, which aims for equal numbers of subjects in each treatment for every possible combination of the interested variables, the minimization method restricts its aim to equalizing treatment numbers at the different levels of each variable taken separately [20; 77]. Essential for this study, the procedure allows sequential assignment of subjects. This method has been shown to be superior to both simple and

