## **E) Blinding Strategy and Assessment**

In addition to the double blinding A/P coil, several blinding strategies will be applied to minimize biases in the study: 1) All subjects are allowed to visualize the TMS coil over the cortical treatment sites on a projected screen and hear the clicking noise during either active or sham rTMS; 2) Standard instruction before and after each rTMS treatment will be given to each subject to minimize instructional related study biases; 3) The procedure for determining the RMT will be identical for each subject. To ensure adequate blinding throughout the study, all subjects will be surveyed whether they receive active-rTMS (Groups A) vs. sham-rTMS (Group B) at Visits 5, 8 and 14; and 4) To minimize investigators' bias, the study coordinator responsible for assessment will go through extensive training by the study PI prior to enrollment of any subjects on both the protocol and administration of assessments. The inter-rater reliability (an intra-class correlation coefficient of  $\geq 0.90$ ) between the study coordinator and the gold standard will be established by the PI. This reliability will be monitored every six months by study statistician, [name]. Both the study coordinator and the investigators will be blinded to the treatment given to the subject. The randomization list will be provided by the study biostatistician. In addition, all data collected will be organized and sent directly to the biostatistician for analysis without going through the PI or any other investigators.

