## **Data Management, Analysis and Power Calculations:**

Missing data values will be minimized by intensive training of the staff involved in the study. Missing data will be examined to assess randomness and the pattern of missing data according to the procedure recommended by Little and Rubin [47]. The investigators will test whether the dropouts are random or systematic by comparing the dropouts with the study completers on the baseline data. An absence of significant differences would support the random nature of dropouts.

Initially, descriptive statistics and exploratory graphing such as frequencies, means, standard deviations, box and whisker plots, stem and leaf diagrams, and scatter plots will be used to assess the normality of the data in terms of the presence of skew and/or outliers. The continuous outcome data will be transformed if necessary by using an appropriate transformation such as the log transform for skewed long tailed data. Similarly, potential covariates will also be summarized with descriptive statistics and graphs to determine the most appropriate way to treat these variables and to decide if a continuous, categorical, or an interval representation is the most appropriate approach.

Data acquired in this project will be managed and analyzed by the study statistician, [name]. Customized database system will be developed for this project to ensure the highest possible data reliability by the study biostatistician. The system will include but is not restricted to: (i) patient demographic input and query; (ii) patient recruitment, scheduling and protocol tracking; (iii) data storage, compilation, selection, and summary transfer to various statistical and graphical sub-systems; (iv) administrative document and report management and, (v) data backup and archival control. Data entry programs will include item prompts, skip patterns, range checks, and logical validity routines. Standard data security protocol will be used for this project. These include, but are not limited to: assigning a unique ID number for each subject, storing confidential information in an encrypted form, using VA secure server, limiting accessibility of data to authorized Center personnel. An electronic archive of all data is kept offsite to insure against loss by fire, theft, etc. All statistical transfer routines are inherently secure via their operating platform and they contain no patient names or personal data.

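### The role that holds the unblinded allocation list appears also to analyse the data, while the primary scale and covariates stay open until the data have been seen

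*Combined protocol and SAP*

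**What the plan says.** **Who holds the codes and who analyses.** In Section 9, *Process of randomization and treatment double blinding*, "The un-blinded study biostatistician" prepares the list, and its codes state which arm is active and which is sham. Under *Blinding Strategy and Assessment*, "The randomization list will be provided by the study biostatistician"; the next sentence adds that "all data collected will be organized and sent directly to the biostatistician for analysis", bypassing the investigators. *Data Management, Analysis and Power Calculations* adds: "Data acquired in this project will be managed and analyzed by the study statistician". Blinding is promised for subjects, investigators and the study coordinator. It is not promised for the analyst.

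**What is left open.** After descriptive statistics and graphs, "The continuous outcome data will be transformed if necessary by using an appropriate transformation such as the log transform for skewed long tailed data". No threshold is given, no transformation is fixed, and the primary outcome is not exempted. Covariates are graphed in the same way "to decide if a continuous, categorical, or an interval representation is the most appropriate approach". The *Statistical Analysis* text under Hypothesis #1 allows adjustment for patient characteristics without listing them. Section 7, *PTSD and MTBI*, makes adjustment for CAPS depend on a significant baseline difference between the groups.

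**What is already fixed.** The primary outcome (diary average over B1 to B6), the mixed model, a saturated treatment-by-time mean structure, selection of the covariance structure by AIC, and Kenward-Roger degrees of freedom.

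**The concern.** The trial takes great care to blind patients and raters to a sham coil, because the outcome is self-rated pain. The analysis stage has no matching protection. If the person who settles the outcome scale, the covariates and their coding can see the arm labels, those choices can be steered by the treatment comparison, knowingly or not. A reader of the final report could not tell whether this had happened.

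The planned Westfall-Young maxT correction does not help. It adjusts across different outcomes, not across alternative versions of the same primary analysis. What is at stake is the credibility of the 0.05 level for the primary comparison, and a result that can be defended as prespecified.

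**Working it through.** **1. The plan's own figure.** The plan states 85% power with 64 per group and 20% dropout, for a difference rising linearly from 0 to 0.5 SD. Under compound symmetry with correlation 0.5 and six periods:

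- Completers per group: 64 × 0.8 = 51.2, taken as 51.
- Slope difference per period: 0.5 / 5 = 0.1.
- Sum of squared centred times: 2 × (2.5² + 1.5² + 0.5²) = 17.5.
- SE² = 2(1 − 0.5) / (51 × 17.5) = 0.00112, so SE = 0.0335.
- 0.1 / 0.0335 = 2.99; 2.99 − 1.96 = 1.03, giving 84.8% power.

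The stated figure reproduces, so the model and time structure have been read as intended. The point below does not depend on it.

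**2. Counting the open choices.** Raw or log scale, baseline continuous or categorical, CAPS in or out: 2 × 2 × 2 = 8 versions of the primary test.

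**3. Type I error with no true effect.** For each simulated null trial, compute the p-value for every version. The error rate of an analyst who keeps the best one is the share of trials in which the smallest p-value is below 0.05. From the plan: 64 per arm, correlations 0.2, 0.5 and 0.8, two-sided 0.05. Assumed: bounded 0–10 scores, symmetric or right-skewed; log(x + 1) as the log transform; a CAPS-type covariate; linear models.

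| How the version is chosen | Run of 6,000 trials per setting | Range over all runs |
|---|---|---|
| One model fixed in advance | 4.7–5.7% | 4.5–5.7% |
| Stated triggers: least pooled skew; CAPS only if baseline p < 0.05 | not in this run | 4.3–5.5% |
| Smallest p of raw and log | 6.3–7.1% | 5.4–7.6% |
| Smallest p of all eight | 7.8–10.7% | 7.3–12.0% |

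Monte Carlo standard error at 5% with 6,000 trials: √(0.05 × 0.95 / 6,000) = 0.28 points.

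Other sets of versions behave alike. Three transformations (raw, log, square root) gave 5.6–7.1%. The same three crossed with four covariate forms gave 6.4–8.2%. A last-time-point ANCOVA with 18 versions gave 7.9–10.7%.

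**4. Why the inflation is moderate.** Eight independent tests would give 1 − 0.95⁸ = 33.7%. The eight versions here use the same patients and are highly correlated, so the rise is much smaller.

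**The case against.** **The figures are not the error rate of the plan as written.** This stands. The plan ties transformation to skewness and outliers, and CAPS to a baseline imbalance. Following those triggers on pooled data keeps the error near 5%. A reader might infer that the plan has an error rate of 8% or 12%, or that selection is intended. The documents support neither. What remains is that the triggers have no threshold, the text does not say whether the graphs are pooled or by arm, and nothing enforces masking.

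**Some of the eight versions are not stated primary options.** This also stands. Baseline severity is named as a covariate only for the second exploratory aim, the CAPS imbalance is not expected, and the simulations used linear models, not the planned mixed model. The range is therefore indicative.

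**List holder and analyst may be two people, and no chooser is named.** Partly right. The sentences on transformation are passive, and the role is called both biostatistician and statistician. But the list and the data go to the biostatistician in consecutive sentences, the investigators are kept out of the data flow, and no second statistician is described. Even with two people, no step withholds the codes from the analyst.

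**A reader might infer that transformation is unnecessary because p-values come from a permutation test.** The documents do not say this. They present maxT as a multiplicity correction, and primary inference rests on a mixed model with Kenward-Roger degrees of freedom. A transformation could still improve efficiency under skew.

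**A reader might also argue that headache-free periods, scoring 0, rule out the log.** This is weak. The log is given only as an example, an offset deals with zeros, and the exacerbation composite, a secondary outcome, is the more obvious target.

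**Conclusion.** The concern holds in a limited form. The documents indicate that the role with the treatment-revealing list also analyses the data. They leave the primary scale, the covariate set and the covariate form to be settled after inspection, with no masking of the analyst and no lock before the codes are merged. The main structure of the primary analysis is already fixed.

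The exposure is moderate. Type I error is near 5% if the stated triggers are applied to pooled data. In the worst case of keeping the smallest p-value with arm labels in hand, it is about 5.5–7.5% for raw or log and about 7.5–12% for eight variants. Per 1,000 null trials, that is 55 to 75 or 75 to 120 false positives instead of 50. These figures rest on assumed score distributions and an assumed set of variants. They show an opening for selection and are no evidence that it occurred. The planned sample size is unaffected. The change should be made, because it costs almost nothing.

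**What to change.** State in the plan now:

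1. The primary analysis uses the untransformed 0–10 diary score in the planned mixed model, adjusted for the four minimisation factors (mechanism of injury, gender, headache severity, past failed therapies) as used at randomisation.
2. Baseline enters once: either B1 stays among the responses, or baseline is a covariate and B1 is removed from the responses. (The text does not define B1; this takes it to be the pre-treatment diary period.) Doing both would use baseline twice.
3. Whether CAPS is a covariate, and in what form, is decided now and not by a between-group significance test at baseline.
4. Any transformed analysis is reported as a sensitivity analysis.
5. Any remaining choice is made on pooled data without the allocation column, and is documented and dated before the codes are merged.

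The cost is a few sentences in the analysis section, with no extra patients or visits. The downside is less freedom to react to skewed scores, with some possible loss of efficiency.

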For hypotheses 1 and 2, where multiple analyses are conducted, correction for family-wise Type I error rates will be made using the Westfall-Young randomization maxTprocedure, which adjusts p-values for significance while taking into account the correlation of the outcomes [76]. In this way, the study can control for an overall family-wise error rate of .05 while achieving more power than Bonferroni adjustments. Using this method of power analysis, the investigators estimated a sample size of 128 (64 per group, accounted for a 20% dropout rate) provides the study with 85% power

to detect a medium effect size (RMASS program provided by Hedeker) [25; 26]. Medium effect sizes were used based on the results included in the above sections. Medium effect size is defined as a between-group difference increasing linearly from 0 at baseline to .5 SD units at the last time point. The minimum power estimation is based on sample size calculation for 10% and 20% attrition, correlations of 0.2, 0.5, and 0.8 between the repeated measures, and for medium and large effect sizes. Data will be analyzed using SPSS version 23, all analyses will be two-tailed, where applicable with  $\alpha = .05$ .

**Hypothesis #1:** Active rTMS at LMC provides significantly more reduction in headache intensity, duration and frequency of exacerbation than sham rTMS.

Independent Variables: Treatment Groups with two levels (Groups A & B), Visits up to 8 (See below). Dependent Variables: Primary outcome: Average daily headache assessments (B1, B2, B3, B4, B5, B6); Secondary outcome: Debilitating Headache Composite Score (B1, B2, B3, B4, B5, B6); M-VAS Scores of headache (Visits 2, 7, 12, 13, 14, 15, 16, 17); HTL-6 and NSI (Visits 2,13,14,15, 16, 17); headache rescue medication usage (Visits 2,13, 14, 15,16, 17). Note, not all variables are collected at all visits.

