increased power to detect effects and precision for the estimation of the effect sizes without requiring increased sample size, and provide the study with a uniform method of data analysis for all hypotheses that include multiple measurements from the same subjects. The mixed effects model method provides an estimate of the individual variability around the population trend, the variability of the individual intercepts (baseline values) and slopes (changes across time), and the correlation between them. A fully saturated treatment by time model will be utilized for inference. Co-variance structure will be chosen based on Akaike's Information Criterion (AIC). This allows for any group level effects to be incorporated into the model. Denominator degrees of freedom will be calculated using the Kenward-Roger small sample correction. Analyses will be conducted within and across nested levels of the study design; this will involve within-subject analyses (comparison of occasions of measurement nested within an individual), as well as between-subject analyses (comparison of two groups). In addition, any treatment group comparison can be adjusted for subject-specific characteristics and adjustments for changes in these characteristics over the course of the study, and incorporated into the single-subject analyses. Based on investigators' experience with previously completed studies, we expect a dropout rate of 10 to 20% throughout the study. All analyses will be two-tailed, where applicable, with  $\alpha = .05$ . Correction for family-wise Type I error rates will be made using the Westfall-Young randomization maxT procedure, which adjusts p-values for significance while taking into account the correlation of the outcomes [70]. In this way we can control for an overall family-wise error rate of .05 while achieving more power than Bonferroni adjustments.

**Hypothesis #2:** Active rTMS at LMC provides significantly more improvement in quality of life, mood and functions than sham LMC stimulations.

Independent Variables: Treatment Groups with two levels (Groups A & B), Visits with 8 levels: pre-treatment (Visit 2), treatment (Visits 7 & 12), and Post-treatment (Visits 13, 14, 15, 16, 17).

Dependent Variables: Attention (CPT II), Memory (Hopkins Verbal Learning Test) Execute function (Trail Making Test A and B, and Stroop Test), Hamilton Depression Scale, SF-36 and BPI.

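### The plan neither exempts the single primary outcome from the maxT correction nor says which alpha gave the 85% power; if the primary is corrected and the 85% used 0.05, power at repeated-measures correlation 0.5 is about 54-78%

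*Combined protocol and SAP*

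**What the plan says.** Section 9, under Data Management, Analysis and Power Calculations, sets the scope of the correction: "For hypotheses 1 and 2, where multiple analyses are conducted, correction for family-wise Type I error rates will be made". The same sentence names the method: "correction for family-wise Type I error rates will be made using the Westfall-Young randomization maxTprocedure". It adds that "the study can control for an overall family-wise error rate of .05 while achieving more power than Bonferroni adjustments". The next sentence gives the power and begins "Using this method of power analysis, the investigators estimated a sample size of 128". In full, the claim is that "a sample size of 128 (64 per group, accounted for a 20% dropout rate) provides the study with 85% power" for a medium effect, defined as a difference growing linearly from zero at baseline to 0.5 SD at the last time point. The inputs listed for the power work are attrition of 10% and 20%, repeated-measures correlations of 0.2, 0.5 and 0.8, and medium and large effects. The only alpha printed is .05: "all analyses will be two-tailed, where applicable with" that value.

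Under hypothesis 1 the same section names one primary outcome, the diary average over six periods (B1 to B6), and five secondary outcomes. The Statistical Analysis text for hypothesis 1 then repeats: "Correction for family-wise Type I error rates will be made using the Westfall-Young randomization maxT procedure". Hypothesis 2 has its own list of outcomes and a claimed minimum power of 85%.

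**The concern.** A single primary outcome named in advance needs no multiplicity adjustment for the secondaries. Placing it in the same maxT family is valid, but the main comparison then pays for up to 13 other outcomes. If the sample size was computed at 0.05 and the test is run at a stricter threshold, the quoted power does not belong to the planned test, and a true effect of the planned size is more likely to be missed. In a joint family, the primary's adjusted p-value also depends on which secondary tests were kept. The COVID-19 revision drops the Stroop, CPT II and Trail Making tests, so that membership has already changed.

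**Working it through.** **Inputs from the plan.** 64 per arm; 20% dropout, so 64 x 0.8 = 51.2 per arm; six diary periods; difference rising linearly to 0.5 SD; repeated-measures correlation rho = 0.2, 0.5 or 0.8; two-sided 0.05. The Research Design paragraph attaches 36% to the same 128, but 200 x 0.64 = 128, which fits the step from consent to randomization. I therefore use 20% after randomization.

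**Family size K.** Hypothesis 1 has the primary plus the exacerbation composite, M-VAS, HIT-6, NSI and rescue medication, so K = 6. Hypothesis 2 adds 7 or 8 (Trail Making A and B counted as one or two, SF-36 as one), so a joint family has K = 13 or 14. Each outcome is assumed to contribute one test.

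**Not in the plan, assumed.** Equal correlation r between the outcomes' test statistics, from 0.2 to 0.8.

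**Step 1: reproduce the 85%.** Use a linear group-by-time contrast c with compound symmetry and power = Phi(delta - critical value), where delta = c'mu / sqrt(2 c'Vc / n). With time coded 0 to 5, c'c = 17.5, c'mu = 0.5 x 17.5 / 5 = 1.75 and c'Vc = (1 - rho) x 17.5.

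- rho = 0.5: c'Vc = 8.75; delta = 1.75 / sqrt(17.5 / 51.2) = 2.993; power = Phi(2.993 - 1.960) = 84.9%.
- rho = 0.2: c'Vc = 14; delta = 2.366; power = 65.8%.
- rho = 0.8: c'Vc = 3.5; delta = 4.733; power = 99.7%.

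The stated 85% is matched at rho = 0.5 with no correction. Spreading the 20% dropout gradually instead gives about 87-88%.

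**Step 2: single-step maxT.** The critical value is the 95th percentile of max|Z| over K equally correlated statistics.

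| K | r | critical z | per-test alpha | power, rho 0.2 | power, rho 0.5 | power, rho 0.8 |
|---|---|---|---|---|---|---|
| 6 | 0.2 | 2.622 | 0.009 | 39.9% | 64.5% | 98.3% |
| 6 | 0.5 | 2.567 | 0.010 | 42.1% | 66.5% | 98.5% |
| 6 | 0.8 | 2.413 | 0.016 | 48.1% | 71.9% | 99.0% |
| 14 | 0.2 | 2.893 | 0.004 | 29.9% | 54.0% | 96.7% |
| 14 | 0.5 | 2.810 | 0.005 | 32.9% | 57.3% | 97.3% |
| 14 | 0.8 | 2.585 | 0.010 | 41.4% | 65.9% | 98.4% |

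For example, K = 6 and r = 0.5 at rho = 0.5: Phi(2.993 - 2.567) = Phi(0.426) = 66.5%.

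**Step 3: step-down maxT** (100,000 simulated trials, rho = 0.5, r = 0.3 to 0.8). If every outcome has the same standardized effect, the primary is rejected in 76-78% of trials (K = 6) or 67-73% (K = 13-14). If only the primary is affected, step-down gives almost no gain over single-step: 65-72% for K = 6 and 54-66% for K = 14.

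**Step 4: could the 85% already be adjusted?** Take eight time points, 10% dropout, rho = 0.5, K = 6 and r = 0.5. Counting completers only (n = 57.6): c'mu = 3, c'Vc = 21, delta = 3 / sqrt(42 / 57.6) = 3.513, and power = Phi(3.513 - 2.567) = 82.8%. With gradual dropout, which keeps partial data, it is about 84-85%. So an adjusted calculation can also land near 85%, but with eight time points rather than the primary's six, and 10% rather than 20% dropout.

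**The case against.** A reader might infer that the primary is definitely tested far below 0.05 and lacks 85% power. The documents do not support that, for four reasons.

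- **Family.** Its members are never listed, and one joint family or one per hypothesis is not stated. The COVID-19 assessment text assigns the attention and executive tests to the secondary hypothesis, apart from the primary aim. This weakens the 14-outcome reading.
- **Variant.** Under step-down maxT the primary's threshold depends on its rank and can rise to 0.05.
- **Alpha behind the 85%.** The power sentence follows directly on the maxT text and can be read as including it; step 4 shows that this is numerically possible.
- **The plan's own grid.** At rho = 0.8 power stays at 96.7% or more after any of these corrections. At rho = 0.2 it is about 66% with none, so that shortfall is not due to maxT alone.

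It is also fair to say that correcting the primary does not inflate false positives, and that highly correlated headache measures (diary and M-VAS cover the same periods) soften the penalty.

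All of this stands and makes the size conditional. It does not settle the threshold for the confirmatory test. The unadjusted reading also remains the more likely one. Power after maxT needs a number of outcomes and a between-outcome correlation, and the power text gives neither. The same 85% is also claimed for hypothesis 2, whose outcome count differs.

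**Conclusion.** The concern holds in conditional form. The plan does not exempt its one primary outcome from maxT, and leaves undefined the family, the variant and the alpha behind the 85%. If the primary is in the family and the 85% used 0.05, the loss at rho = 0.5 is roughly 13 to 31 percentage points with single-step maxT (84.9% down to 71.9% at best and 54.0% at worst). With step-down and equal effects on all outcomes it is roughly 7 to 18 points. These figures rest on the linear-trend contrast, compound symmetry, one test per outcome, and the assumed between-outcome correlations (0.2 to 0.8 for single-step, 0.3 to 0.8 for step-down). It would be too strong to conclude that the trial is underpowered: that depends on a repeated-measures correlation for which the plan gives only a range, and on choices it has not stated.

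**What to change.** State that the diary primary is tested alone at two-sided 0.05. If it is significant, apply maxT at 0.05 to the secondary outcomes of hypotheses 1 and 2 as one listed family, naming single-step or step-down. Overall family-wise error stays at 0.05, and the 85% stands at rho = 0.5. This changes wording only, with no added patients, visits or data. The price is that no confirmatory secondary claim can be made if the primary fails.

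If the primary is to stay in the family, list the family, name the variant, give the adjusted alpha and the assumed between-outcome correlation, and restate the power. That route may not be free. Per arm, n = ((critical z + 1.036) / 0.4183)^2 / 0.8, where 0.4183 = 2.993 / sqrt(51.2). At rho = 0.5 and r from 0.3 to 0.8, 85% power under single-step maxT needs about 170-190 randomized for 6 outcomes, or 188-220 for 14. The same formula gives 130 without correction, against the planned 128.

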Our group was the first in the VA system to adopt brain magnetic resonance imaging (MRI) neuronavigation guided repetitive transcranial magnetic stimulation (rTMS) as a non-invasive treatment option for chronic pain including MTBI-HA in 2010. Our prospective follow-up survey indicated over 150 patients with MTBI-HA treated with rTMS demonstrated over 50% reduction in headache intensity with correlated reduction (>50%) in the frequency and duration of debilitating headache exacerbation. Close to 90% of these initial treatment responsive patients are currently on a maintenance treatment protocol, which continues to demonstrate sustainable headache prevention and relief benefit. This ongoing clinical observation supports the feasibility of using rTMS for long-term headache management in patients with MTBI-HA. *Further support for adopting this innovative therapy for MTBI-HA comes from our recently completed randomized sham controlled study indicating an initial week long course (3 sessions) of rTMS at the left motor cortex (LMC) can alleviate MTB related headache symptoms and reduce the exacerbation pattern for up to one month without significant side effects. 80% of the patients received the real treatment demonstrated at least 50% headache reduction in comparison to only 20% of the patients in the sham group [43]. For long-term management, published case series show subsequent maintenance treatment sessions can be feasibly applied at a much lesser frequency than the initial sessions of rTMS with sustainable headache relief benefit [41; 81]. Coinciding with other published treatment protocols related to traumatic brain injury and pain [32; 55], this initial clinical evidence provides compelling support for the current proposal aiming to assess the effect of a longer duration of rTMS protocol in managing MTBI-HA for up to 10 weeks after the initiation of the treatment.* Given existing treatment options for MTBI-HA are limited, validating such a non-pharmacological and non-invasive treatment option will significantly enhance the capability of the VA healthcare system in caring for this rapidly increasing patient population.

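### The 85% power matches a one-degree-of-freedom linear trend, but the saturated treatment-by-time model names no primary contrast; if its 5-df test decides Hypothesis 1, power is about 62-63% on the same assumptions

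*Combined protocol and SAP*

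**What the plan says.** Section 9, under the heading Data Management, Analysis and Power Calculations, reports that "a sample size of 128 (64 per group, accounted for a 20% dropout rate) provides the study with 85% power" to detect a medium effect. The effect is defined in the same paragraph: "Medium effect size is defined as a between-group difference increasing linearly from 0 at baseline to .5 SD units at the last time point". The calculation is described as covering "sample size calculation for 10% and 20% attrition" and "correlations of 0.2, 0.5, and 0.8 between the repeated measures". The paragraph does not say which of these gave 85%, what covariance structure was used, or how many degrees of freedom the powered test has.

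The outcome for Hypothesis 1 is listed there as "Primary outcome: Average daily headache assessments (B1, B2, B3, B4, B5, B6", that is, six between-visit diary periods.

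The Statistical Analysis text for Hypothesis 1 first describes each patient's course by an intercept and a slope. It then says: "A fully saturated treatment by time model will be utilized for inference". The covariance structure is to be selected by AIC, with Kenward-Roger degrees of freedom. No sentence says whether Hypothesis 1 is decided by the overall treatment-by-time interaction, a linear-trend contrast, an average over periods, or the difference at one period.

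**The concern.** The planning effect is a single straight line, and a straight-line difference is tested most directly with one degree of freedom. With six periods, the treatment-by-time term of a saturated model has five. An overall test on five degrees of freedom spreads its sensitivity over every possible pattern, so it needs a larger signal to reach the same power. The power statement and the inference statement may therefore refer to different tests.

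Two things are at stake. The stated power may not belong to the test that decides the primary outcome. And because the saturated model supports several reasonable tests of treatment, leaving the choice open allows it to be made after the data are seen.

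**Working it through.** **Inputs from the documents.** 64 per group; 20% attrition (10% also considered); difference rising linearly from 0 to 0.5 SD; six periods B1 to B6; correlations 0.2, 0.5 and 0.8; two-sided alpha 0.05; 1:1 allocation.

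**Inputs assumed here.** B1 is the baseline period; periods are equally spaced; covariance is compound symmetric; correlation is 0.5 unless stated; no multiplicity adjustment.

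**Step 1: reproduce the 85%.** Scale time to 0, 0.2, ..., 1. Then Sxx = 2 x (0.25 + 0.09 + 0.01) = 0.70. The variance of the difference in slopes is 2(1 - rho)/(n x Sxx). With 64 x 0.8 = 51.2 per group and rho = 0.5, this is 1/(51.2 x 0.70) = 0.0279, so the SE is 0.167. The ratio 0.5/0.167 is 2.99, the noncentrality is 2.99 squared = 8.96, and power is Phi(2.99 - 1.96) = 84.9%. Working backwards, 85% needs 52 per group, and 52/0.8 = 65, one more than the stated 64. If dropout is instead gradual and linear from 64 to 51.2 per group (generalised least squares, noncentral t with 2 x 64 - 2 = 126 df), the linear contrast within the saturated model has 86.6%.

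**Step 2: the 5-df test on the same inputs.** When the true difference is exactly linear, the overall treatment-by-time test has the same noncentrality as the slope test; only the degrees of freedom change. With noncentrality 8.96 and the chi-square critical value 11.07 on 5 df, power is 62.1%. With gradual dropout the noncentrality is 9.60, and the noncentral F(5, 126) gives 63.4%.

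**Step 3: vary the correlation and attrition.**

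| Correlation | Linear trend, 51.2 per group | 5-df test, 51.2 per group | Linear contrast, gradual dropout | 5-df test, gradual dropout |
|---|---|---|---|---|
| 0.2 | 65.8% | 40.5% | 68.8% | 42.3% |
| 0.5 | 84.9% | 62.1% | 86.6% | 63.4% |
| 0.8 | 99.7% | 97.2% | 99.8% | 97.4% |

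At 10% gradual attrition and correlation 0.5, the figures are 89.2% and 67.5%.

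**Step 4: take the 85% as given.** If 85% is a 1-df figure, its noncentrality is (1.960 + 1.036) squared = 8.98, however it arose. For a linear effect, the 5-df test then has 62.2% (chi-square), or 59.5% to 61.7% as an F test with 100 to 510 denominator df. To reach 85% on 5 df, noncentrality must be 14.39. The ratio 14.39/8.98 = 1.60 implies about 128 x 1.60 = 205 randomised.

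**Step 5: candidate tests within the saturated model** (gradual dropout, correlation 0.5). The plateau is 0.5 SD in every period from B2 to B6.

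| Test | Linear growth | Plateau |
|---|---|---|
| Linear contrast, 1 df | 86.6% | 59.2% |
| Mean of B2 to B6 minus B1, 1 df | 56.3% | 94.2% |
| Treatment-by-time, 5 df | 63.4% | 77.4% |

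**The case against.** The strongest reply is that the 5-df test is a reader's construction. A saturated model fixes the mean structure; it does not fix the decision rule. It supports 1-df contrasts, its linear contrast keeps the claimed power, and the surrounding text speaks of slopes. This stands. A reader might infer that the trial has planned an omnibus test and would miss more than one true effect in three. The documents do not say so.

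A second reply is that correlation 0.5, compound symmetry and equal spacing are not the plan's stated basis, and that follow-up visits are not evenly spaced. This also stands. With gradual 20% dropout the 5-df test reaches 81% at correlation 0.65 and 87% at 0.70, both inside the plan's range. So it cannot be said that 85% is attainable only with a trend test. That 85% is a 1-df figure is an inference from the effect definition and from the reproduction.

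A third temptation is to argue that benefit must fade once treatment ends, because the Background says "Close to 90% of these initial treatment responsive patients are currently on a maintenance treatment protocol" and this trial gives no sessions during follow-up. That sentence describes a clinical follow-up series; it does not establish fading within this trial. The Background to Section 7 also expects longer benefit from ten sessions than from three. A fade from 0.5 to 0.1 SD would leave the linear contrast with about 7% power, but no section gives that profile, so it serves only as an illustration of sensitivity to shape.

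None of these replies supplies the missing statement of which test decides Hypothesis 1.

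**Conclusion.** The point holds as a gap in specification with a consequence for power. The arithmetic behind 85% is sound for a linear trend at correlation 0.5. What is missing is the test to which that figure applies. Under the planning effect, at correlation 0.5 with 20% gradual attrition, the three tests compared range from 56% to 87%, and the natural overall test of the stated model sits at about 62% to 63%. The drop from 85% to roughly 60% to 62% follows for any linear effect once 85% on 1 df is granted. The absolute figures rest on the assumed correlation, covariance and spacing, and run from about 42% to 97% for the 5-df test over the plan's own correlations. Any figure that falls under the planned Westfall-Young correction would be lower.

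The documents do not support simply replacing 85% by 63%: that would be right only if the omnibus test is intended and correlation 0.5 was the planning value.

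**What to change.** In the Statistical Analysis text for Hypothesis 1, keep the saturated means model and name, before unblinding, one 1-df primary contrast on B1 to B6. The linear contrast is the one that matches the stated 85%. The mean of B2 to B6 minus B1 is more robust to an early plateau (94% against 59%) but weaker under linear growth (56% against 87%). The choice should follow the course the sponsor expects.

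In the power paragraph, state the correlation, covariance structure and time spacing used, and quote the power of the named contrast. If the overall 5-df test is intended, replace 85% with its power across the plan's correlations.

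The cost is a few lines of text. Naming a contrast and restating its power needs no additional patients. The price is that the stated power may be less favourable; holding 85% on the 5-df test would take about 205 randomised under the assumptions above.
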